**Number of Subjects Planned:**

It is planned to enroll 40 healthy adult subjects into up to 5 cohorts of 8 subjects each in Part 1 (SAD) to ensure data in a minimum of 6 evaluable subjects per cohort. Up to 2 replacement subjects per cohort may be enrolled into Part 1 of the study.

It is planned to enroll up to 48 healthy adult subjects into up to 4 cohorts of 12 subjects each (MAD Cohort 4 is optional) in Part 2 (MAD) to ensure data in a minimum of 8 evaluable subjects per cohort. Up to 3 replacement subjects per cohort may be enrolled into Part 2 of the study.

See [Section 8.4](#) for further details.

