**Figure 1 Study Sequence: Part 1 Single Ascending Doses****8.1.2 Study Plan: Part 2 Multiple Ascending Doses**

Part 2 is a double-blind, randomized, placebo-controlled assessment of SC PDM608 MAD administrations. Subjects will be enrolled sequentially into 1 of up to 4 cohorts, each containing 12 subjects. Within each cohort, 9 subjects will be randomly assigned to receive PDM608 and 3 subjects will be randomly assigned to receive matching placebo. MAD Cohort 4 is optional; the decision on whether to dose this cohort will be based on interim review of preceding MAD Cohorts 1 to 3.

Part 2 may be dosed in parallel with Part 1, but can only proceed following interim review of safety and tolerability data from at least the first 3 SAD cohorts in Part 1. Dosing for each MAD cohort will be at a dose level 2-3 fold lower than the highest SAD cohort dose deemed safe by the SAC at the time of each MAD cohort initiation.

An evaluable subject for Part 2 is defined as a subject who has received all 4 doses of IMP and undergone all safety and tolerability assessments out to 96 hours post-final dose (dose 4). Sentinel dosing is not planned for MAD cohorts, but the SAC may implement a sentinel design if deemed appropriate.

Following completion of each cohort, the safety and tolerability assessments out to 96 hours post-final dose (Day 26) will be reviewed to determine whether to progress to the next dose level and the dose to be administered. Full details of the interim data reviews are provided in [Section 8.2](#).

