### 8.2.2 Criteria for Dose Decision

Progression to the next dose group will be permitted after review of defined safety and tolerability data suggests that it is safe to do so. All SAC decisions will be documented and signed by the investigator and Sponsor medical monitor or delegate. Evidence of the decision will be retained in the Trial Master File (TMF).

For dose escalation in the SAD phase to proceed data must be available from a minimum of 6 subjects who have completed the planned safety and tolerability assessments out to 96 hours post-dose (Day 5), to ensure at least 4 subjects receive active IMP. For dose escalation in the MAD phase to proceed data must be available from a minimum of 8 subjects who have completed the planned safety and tolerability assessments out to 96 hours post-final dose (Day 26) to ensure at least 6 subjects receive active IMP.

It is planned that the dose will be escalated for each subsequent cohort; however, the SAC may also agree to enroll additional subjects for an intermediate dose level if warranted or may agree to reduce the dose with no limit on the possible extent of reduction. Any decision to investigate an intermediate or reduced dose level will be fully documented.

The decision to proceed to the next dose level will be based on safety and tolerability and data. The following data are required:

- AEs
- Vital signs
- Safety laboratory, including review of PD hematology parameters outlined in [Section 6.4](#)

- 12-lead ECG
- Physical examinations

The SAC may also consider additional data as it becomes available and as relevant to decisions, including ADA, PD, and PK.

Rules for dose decision are as follows:

- Dose escalation will not be more than 3-fold between SAD cohorts. Anticipated SAD dose levels are described in [Table 2](#).
- Dose escalation will not be more than 3-fold between MAD cohorts.
- Dosing for each MAD cohort will be at a dose level 2-3 fold lower than the highest SAD cohort dose deemed safe by the SAC at the time of each MAD cohort initiation.
- Doses administered will be predicted not to exceed a mean  $C_{max}$  of 103,950 ng/mL and a mean  $AUC_{(0-24h)}$  of 1,775,000 ng.h/mL, which is the sex-averaged mean NOAEL exposure limits after the first dose of 18 mg/kg in the cynomolgus NOAEL 28-day good laboratory practice (GLP) toxicology study, in any individual subject.

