## 8.8 Subject Selection List and Randomization

This is a double-blind, randomized, placebo-controlled study; therefore, a randomization schedule will be produced for each study part.

A subject selection list will be produced for each study part prior to dosing using the randomization schedule and will be retained in the Investigative Site File (ISF).

In Part 1, for sentinel dosing, a group of 2 subjects will be dosed ahead of the remaining subjects in each cohort. A randomization schedule will be used such that the first 2 subject numbers will be allocated to active or placebo in a 1:1 ratio (i.e., 1 subject will be randomly assigned to receive PDM608 and 1 subject will be randomly assigned to receive matching placebo). The remaining 6 subject numbers will be allocated to active or placebo in a 5:1 ratio (i.e., 5 subjects will be randomly assigned to receive PDM608 and 1 subject will be randomly assigned to receive matching placebo).

For Part 2, a randomization schedule will be used to allocate subject numbers to PDM608 or placebo in a 3:1 ratio (i.e., in each cohort, 9 subjects will be randomly assigned to receive PDM608 and 3 subjects will be randomly assigned to receive matching placebo).

Subjects will be randomized prior to administration of the first dose.

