#### **8.8.1 Subject Numbers**

Four-digit subject numbers will be allocated prior to initial dosing according to a code established by Quotient. Replacement subjects will be allocated subject numbers where the last three digits are the same as those of the original subject (e.g., if Subject 1005 withdraws, the replacement will have Subject Number 9005 and will receive the same regimen as Subject 1005).

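### Section 8.2.2 says 8 MAD completers ensure at least 6 on active drug; with 9 active and 3 placebo per cohort, they ensure only 5

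*Combined protocol and SAP*

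**What the plan says.** Protocol Section 8.2.2 sets a completer count for each escalation. For the MAD part, "data must be available from a minimum of 8 subjects who have completed the planned safety and tolerability assessments" to Day 26, and the purpose given is a minimum number on active drug: the gate counts those who "completed the planned safety and tolerability assessments out to 96 hours post-final dose (Day 26) to ensure at least 6 subjects receive active IMP". The preceding sentence sets the SAD count at 6 subjects with assessments to "96 hours post-dose (Day 5), to ensure at least 4 subjects receive active IMP".

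Sections 8.1.2 and 8.8 both fix the MAD cohort of 12 at 3:1; in 8.1.2, "9 subjects will be randomly assigned to receive PDM608 and 3 subjects will be randomly assigned to receive matching placebo". Under Section 8.8.1 a replacement for Subject 1005 "will receive the same regimen as Subject 1005". Section 8.4 allows up to 3 replacements per MAD cohort, but none for a subject withdrawn because of an IMP-related AE.

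The synopsis plans MAD enrollment "to ensure data in a minimum of 8 evaluable subjects per cohort", and Section 14.1 repeats the 8. Neither gives a minimum on active drug. Section 8.1.2 defines an evaluable Part 2 subject as "a subject who has received all 4 doses of IMP and undergone all safety and tolerability assessments out to 96 hours post-final dose". The gate in 8.2.2 does not use the word evaluable.

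**The concern.** The gate presents 6 active subjects as the result of having 8 completers. Under the 9:3 allocation that does not follow, because up to 3 of the 8 can be on placebo. The SAD sentence shows that the plan means a guaranteed minimum, and by that standard the MAD figure is one too high.

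The count is a required condition for every MAD escalation, which may be up to 3-fold, in a first-in-human study with no planned MAD sentinel dosing. The study is double-blind, and the plan requires nobody to count active completers before the Safety Advisory Committee (SAC) decides. A committee that relies on the sentence would believe it had 6 active subjects with complete data when it might have 5. That is most likely when subjects on active drug drop out more often than those on placebo.

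A lesser point is that the gate does not say whether a subject who missed a dose but stayed in follow-up to Day 26 counts. The post-final-dose anchor and the shared minimum of 8 suggest that only evaluable subjects are meant, but the sentence leaves this open.

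**Working it through.** **Inputs.** SAD cohort: 6 active, 2 placebo, minimum 6 completers, stated guarantee 4 (Sections 8.1.1, 8.2.2). MAD cohort: 9 active, 3 placebo, minimum 8 completers, stated guarantee 6 (Sections 8.1.2, 8.8, 8.2.2). Same-regimen replacement (8.8.1) keeps the maximum number of placebo completers at 3, provided that a replaced subject is not counted as well as the replacement.

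**Guaranteed minimum** = required completers - placebo subjects in the cohort.

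- SAD: 6 - 2 = 4. This reproduces the plan's figure.
- MAD: 8 - 3 = 5. The plan says 6.
- MAD with 9 required: 9 - 3 = 6.

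Listing every possible set of completers gives the same three minima.

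**Does an average explain the 6?** For MAD, 8 x 9/12 = 6. For SAD, the same rule gives 6 x 6/8 = 4.5, not the stated 4. Only the worst-case rule fits the SAD figure.

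**How often the gate is met with only 5 active.** Without replacement this requires exactly 5 of 9 active and 3 of 3 placebo subjects to complete. With completion probabilities a (active) and b (placebo):

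P = C(9,5) x a^5 x (1-a)^4 x b^3, where C(9,5) = 126.

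The documents give no completion rates, so these are assumed. At 80% in both arms, P = 126 x 0.8^5 x 0.2^4 x 0.8^3 = 0.0338.

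| Active / placebo completion (assumed) | Gate met with only 5 active |
|---|---|
| 95% / 95% | 0.05% |
| 90% / 90% | 0.5% |
| 85% / 85% | 1.7% |
| 80% / 80% | 3.4% |
| 80% / 100% | 6.6% |
| 67% / 100% | 20% |

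**With replacement.** Assume that every loss is replaceable, up to 3 randomly chosen losses are replaced on the same regimen, and replacements complete at the same rate. The chance of passing with 5 or fewer active becomes 0.007% at 90%/90%, 0.35% at 80%/80%, 0.33% at 80%/100% and 4.8% at 67%/100%.

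**Chance that a cohort of 12 passes, without replacement.**

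| Active / placebo completion (assumed) | As written: 8 or more | 8 or more, with 6 or more active | 9 or more |
|---|---|---|---|
| 90% / 90% | 99.6% | 99.0% | 97.4% |
| 80% / 80% | 92.7% | 89.4% | 79.5% |
| 67% / 100% | 85.5% | 65.0% | 65.0% |

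**The case against.** The strongest reply is that the arithmetic is right but matters little. The gap is one subject, and without replacement it needs exactly 8 of 12 to complete with all 4 losses on active drug. Replacement is part of the plan and, in the favorable case, cuts the probabilities about tenfold or more at 80% completion or better. This stands, and the no-replacement figures are best read as the upper end of a range for a given pair of completion rates. Replacement is optional, however, and is barred after withdrawal for an IMP-related AE, so the true values lie between the two sets. The 67%/100% case is an extreme that nothing in the protocol predicts.

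Other safeguards also apply. The SAC sees AEs from all dosed subjects. One possibly related SAE, or two severe related AEs in the same organ class within a cohort, halts the study. Each MAD dose must be 2-3 fold below the highest SAD dose deemed safe, and exposure caps apply. Section 8.8.2 permits access to assignment if warranted at a safety review, and lets individual data go to the review committee even if they reveal treatment. All of this limits the harm, but none of it requires a count of active completers.

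One could read the 6 as a separate requirement. The sentence presents it as a consequence of the 8, and on that reading a checking procedure would still be missing.

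**Conclusion.** The concern holds. The worst-case count depends only on the 9:3 allocation, same-regimen replacement and the minimum of 8, and it gives 5 active subjects where Section 8.2.2 states 6. No other section sets or checks an active minimum for MAD escalation; the 7-of-9 rule in Sections 6.4 and 8.2.2 governs the pharmacodynamic dose cap.

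The practical effect is small: one active subject with complete data to Day 26, in well under 1% of cohorts at 90% completion in both arms, and in a few percent at most at 80% in both arms. These frequencies rest on assumed completion rates and independent losses. This does not show that 8 completers are too few; it shows that the stated guarantee is false. It should be corrected because it is a required escalation condition and the correction is cheap.

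**What to change.** Make one of three changes in Section 8.2.2, according to which number was intended.

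- **(a) Keep 8 and require at least 6 on active drug**, confirmed to the SAC as yes or no by the unblinded pharmacist or designee already named in Section 8.8.2. That section should then list this task. This secures the 6 with no more failed gates than (c). Its cost is some unblinding: without replacement, a no with 8 of 12 counted tells the SAC that all 4 non-completers were on active drug.
- **(b) Keep 8 and state the guarantee as 5.** This changes one numeral and has no operational cost.
- **(c) Raise the minimum to 9 of 12.** This guarantees 6 without unblinding, but the unreplaced pass rate at 80% completion in both arms falls from 92.7% to 79.5%, against 89.4% under (a). The synopsis and Section 14.1 need the same change.

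Under (a) or (c) some cohorts may wait or fail the gate, because subjects withdrawn for an IMP-related AE cannot be replaced.

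Under any option, as a minor clarification, have the gate count evaluable subjects as defined in Section 8.1.2. A subject who missed a dose would then not count toward the minimum but would stay in the SAC safety review.

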#### **8.4 Subject Replacement**

Up to 2 replacement subjects per cohort may be enrolled into Part 1 (SAD). The maximum number of subjects that may be dosed is 50.

Up to 3 replacement subjects per cohort may be enrolled into Part 2 (MAD). The maximum number of subjects that may be dosed is 60.

Any subject withdrawn due to an IMP-related AE will not be replaced. Subjects withdrawing for other reasons may be replaced as required by agreement between the investigator and Sponsor to ensure sufficient evaluable subjects.

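### Section 8.2.2 says 8 MAD completers ensure at least 6 subjects on active IMP; with 3 placebo slots per cohort they ensure only 5.

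*Combined protocol and SAP*

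**What the plan says.** Section 8.2.2 sets the data needed before a MAD escalation: "For dose escalation in the MAD phase to proceed data must be available from a minimum of 8 subjects", followed through to 96 hours "post-final dose (Day 26) to ensure at least 6 subjects receive active IMP". The single-dose (SAD) sentence just before it requires 6 completers "to ensure at least 4 subjects receive active IMP".

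The allocation is fixed. Section 8.1.2 states that in each MAD cohort "9 subjects will be randomly assigned to receive PDM608 and 3 subjects will be randomly assigned to receive matching placebo", and Section 8.8 repeats the 9 and 3. Replacement does not alter it. In the example in Section 8.8.1, "the replacement will have Subject Number 9005 and will receive the same regimen as Subject 1005". Section 8.4 allows up to 3 replacements per MAD cohort, at the discretion of the investigator and Sponsor, with one exclusion: "Any subject withdrawn due to an IMP-related AE will not be replaced".

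Section 8.2.2 sets no other minimum number of active completers for escalation. Its 7-of-9 condition belongs to the pharmacodynamic dose cap. The Synopsis and Section 14.1 give a minimum of 8 evaluable subjects per MAD cohort, with no split by arm.

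**The concern.** The sentence asserts a guarantee. A guarantee about active subjects has to hold in the worst case, in which every placebo slot completes and all the losses are active. The SAD figure passes that test and the MAD figure is one too high.

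This is the only stated minimum of active completers behind a MAD escalation in a first-in-human study. Sentinel dosing is not planned for MAD cohorts, and the study is blinded. A member of the Safety Advisory Committee (SAC), or an IRB reader, would take it that 8 completers carry at least 6 active subjects. They would not normally see that a given set of 8 carries 5.

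**Working it through.** **Inputs**
- SAD cohort: 6 active, 2 placebo; minimum 6 completers; stated active minimum 4 (Sections 8.1.1 and 8.2.2).
- MAD cohort: 9 active, 3 placebo; minimum 8 completers; stated active minimum 6 (Sections 8.1.2, 8.8 and 8.2.2).
- Replacements keep the regimen of the slot (Section 8.8.1), so at most 3 MAD completers can be on placebo.
- Dropout rate: not given, so assumed below.

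**Guaranteed active subjects** = minimum completers − placebo slots.
- SAD: 6 − 2 = 4. This reproduces the stated figure.
- MAD: 8 − 3 = 5. The stated figure is 6.
- MAD with 9 completers: 9 − 3 = 6.

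The statement is therefore true at 9 or more completers and can fail only at exactly 8. There it fails when all 4 unfilled slots are active (9 − 4 = 5).

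**Conditional chance.** Given exactly 8 of 12 slots completing, with losses random across slots, P(k active) = C(9,k)·C(3,8−k)/C(12,8), and C(12,8) = 495.

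| Active completers | Probability |
|---|---|
| 5 | 126/495 = 25.5% |
| 6 | 50.9% |
| 7 | 21.8% |
| 8 | 1.8% |

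**Unconditional chance per cohort, no replacement.** The event is 4 of 9 active lost and 0 of 3 placebo lost.
- Equal loss p in both arms: C(9,4)·p⁴·(1−p)⁵·(1−p)³ = 126·p⁴·(1−p)⁸.
- Loss p on active and none on placebo: 126·p⁴·(1−p)⁵.

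**With replacement.** Assume equal loss in both arms and every loss replaceable. Up to 3 replacements go to randomly chosen lost slots, and replacements are lost at the same rate p. Exact enumeration of the chance of ending with exactly 4 unfilled slots, all active, gives the last column.

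| Assumed loss p | Equal loss, none replaced | Active loss only, none replaced | Equal loss, up to 3 replaced |
|---|---|---|---|
| 10% | 0.5% | 0.7% | 0.007% |
| 20% | 3.4% | 6.6% | 0.35% |
| 30% | 5.9% | 17.2% | 2.1% |

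For example, at p = 20%: 126 × 0.0016 × 0.1678 = 3.4%, and 126 × 0.0016 × 0.3277 = 6.6%.

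**The case against.** **Six as an expectation.** Under 9:3 allocation, 8 completers contain 8 × 9/12 = 6 active on average. That may be where the figure came from, but the sentence claims an assured minimum, and the SAD figure beside it follows the worst-case subtraction. On the averaging reading the SAD figure would be 6 × 6/8 = 4.5, not 4. This defence does not stand.

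**Practical reach.** This objection largely stands. The failing case needs four unfilled active slots with every placebo slot complete, and replacements exist to prevent such shortfalls. If the losses came from IMP-related adverse events, the SAC would see those events. The halting rules would apply if an event were serious, or if two or more in a cohort were severe and in the same organ system class. The halting rules do not exclude the case altogether: confirmed proteinuria or hematuria requires withdrawal from study drug under Section 8.3 but is not a halting criterion in Section 8.5.

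**Stronger readings that the documents do not support**
- A reader might infer that a safety protection is missing. The requirement of 8 completers stands. So do SAC review, the halting rules, the exposure ceilings, the 3-fold step limit and the rule that each MAD dose is "at a dose level 2-3 fold lower than the highest SAD cohort dose deemed safe by the SAC".
- A reader might take 25.5% as the risk for a cohort. It is conditional on exactly 8 of 12 slots completing.
- A reader might treat the equal-loss figures with and without replacement as the bounds of the true chance. They bound it only under equal loss. IMP-related withdrawals are not replaced and would be expected to fall mainly on active, and the active-only column exceeds the equal-loss figures at every assumed rate.

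**Conclusion.** The stated MAD figure is wrong as written: 8 completers ensure 5 subjects on active IMP, against the 6 claimed. This follows from the fixed allocation and same-regimen replacement, with no assumption about dropout.

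How often the difference would matter cannot be settled from the documents. It rests on assumed loss rates, on how losses divide between arms and on how many are replaced. In the scenarios tabulated above the chance per cohort runs from well under 1% to 17.2%, the latter with 30% loss confined to active and no replacement.

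Severity is minor. The consequence is that an escalation could proceed on one fewer active completer than the text promises, with the other safeguards intact. The documents do not show whether the 8 or the 6 is the slip.

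**What to change.** The sponsor should decide which number was intended and correct Section 8.2.2 accordingly.

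- **Restate the MAD minimum as 5 active.** This changes one number and no operative rule. The Synopsis and Section 14.1 need no edit. The cost is an openly lower stated minimum in a first-in-human study.
- **Require 9 completers**, if 6 active is a real minimum. This must be reconciled with the minimum of 8 evaluable in the Synopsis and Section 14.1. It also blocks escalation at 8 completers when 6 or more are active, which is 369/495 = 74.5% of random-loss cases at that count.
- **Keep 8 completers and have unblinded staff confirm at least 6 active.** Section 8.8.2 already gives the unblinded pharmacist the schedule. A negative answer at exactly 8 completers tells the SAC that all 4 unfilled slots are active. That blinding cost is small, and Section 8.8.2 already tolerates it: it permits access to assignments when scheduled safety reviews warrant it, and individual data for dose selection even where they may reveal treatment.

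Under either of the last two options, four active slots that cannot be filled leave at most 8 completers and 5 active, so escalation stops. If the losses were drug-related, that may be exactly what a minimum is for. The sponsor should say whether it is intended.

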### 8.3 Subject Withdrawal

A subject may withdraw his/her participation from the study at any time or may be discontinued for any of the reasons below. In either case, every reasonable effort will be made by Quotient to complete a final assessment/discharge procedures and to provide medical follow-up as indicated. Quotient will advise the Sponsor of the withdrawal of any subject from the study.

Early withdrawal is defined as the date of the decision to withdraw the subject from the study. Subject completion is defined as the date of the last procedure conducted or last contact (e.g., phone call or unscheduled visit) for that subject.

If a subject requests to leave the clinical unit earlier than the planned discharge time (e.g., due to unforeseen personal circumstances) but aims to return to the clinical unit to complete the study, this will be documented as a subject self-discharge and a protocol deviation. The subject must complete the planned assessments/discharge procedures before discharge from the clinical unit and will return for the next study period/assessments, as planned following agreement between the Sponsor and the investigator.

Part 1 is a single dose assessment; therefore, after an individual subject has received a dose of IMP withdrawal of that subject from further dosing is not possible. Subjects will be monitored for the criteria detailed below which may require their withdrawal from some or all study procedures if continuation is not in their best interests, except when the withdrawal is a result of withdrawal of consent.

Part 2 is a multiple dose assessment; therefore, subjects will be withdrawn from the study drug(s) for the reasons detailed below.

- Experiencing a SAE, severe AE or laboratory abnormality including but not limited to:
  - corrected QT interval by Fridericia's formula (QTcF) interval of >500 msec or increase in QTcF interval of >60 msec from baseline at a value of >450 msec (confirmed following a repeat ECG)
  - alanine aminotransferase (ALT) concentration  $>3 \times$  the upper limit of the reference range (confirmed following a repeat ALT blood test)
  - proteinuria, hematuria and/or hyaline casts in urine (confirmed following a repeat urinalysis)
  - other clinically significant laboratory abnormalities that necessitate study discontinuation in the opinion of the investigator and medical monitor
- Pregnancy
- Termination of the study by the Sponsor, regulatory agency or IRB
- Upon the subject's request (withdrawal of consent)
- Significant deviation from the protocol, as determined by the Investigator and Sponsor
- Significant concurrent illness or requirement for prohibited medication

- Subject non-compliance
- At the discretion of the investigator

Baseline will be considered the last available assessment prior to first dose for the purpose of withdrawal criteria.

Every effort will be made to ensure that subjects who discontinue IMP administration because of an IMP-related AE will complete all safety follow-up procedures.

Early withdrawal for any of the above reasons should be documented and distinguished from withdrawal of consent by the subject to participate in any further activities.

